8 SAFETY ASSESSMENTS

8.1 Adverse Events

An adverse event is defined as any untoward medical occurrence in a subject administered a pharmaceutical product, which does not necessarily have a causal relationship with this treatment. An adverse event can therefore be any unfavorable and/or unintended sign (including an abnormal laboratory finding), symptom, or disease temporally associated with the use of an investigational medicinal product, whether or not related to the investigational medicinal product. All adverse events, including observed or volunteered problems, complaints, or symptoms, are to be recorded on the appropriate eCRF.

Adverse events, which include clinical laboratory test variables, will be monitored and documented from the time of informed consent until study participation is complete. Subjects should be instructed to report any adverse event that they experience to the Investigator. Investigators should make an assessment for adverse events at each visit and record the event on the appropriate adverse event eCRF.

Wherever possible, a specific disease or syndrome rather than individual associated signs and symptoms should be identified by the Investigator and recorded on the eCRF. However, if an observed or reported sign or symptom is not considered a component of a specific disease or syndrome by the Investigator, it should be recorded as a separate adverse event on the eCRF. Additionally, the condition that led to a medical or surgical procedure (eg, surgery, endoscopy, tooth extraction, or transfusion) should be recorded as an adverse event, not the procedure.

Any medical condition already present at the Baseline Visit should not be reported as an adverse event unless the medical condition or signs or symptoms present at baseline change in severity or seriousness at any time during the study. In this case, it should be reported as an adverse event.

Clinically significant abnormal laboratory or other examination findings that are detected during the study or are present at the Baseline Visit and significantly worsen during the study should be reported as adverse events. The Investigator will exercise his or her medical and scientific judgment in deciding whether an abnormal laboratory finding or other abnormal assessment is clinically significant. Clinically significant abnormal laboratory values occurring during the clinical study will be followed until repeat tests return to normal, stabilize, or are no longer clinically significant. Any abnormal test that is determined to be an error does not require reporting as an adverse event.

8.1.1 Adverse (Drug) Reaction

All noxious and unintended responses to a medicinal product related to any dose should be considered an adverse drug reaction. “Responses” to a medicinal product means that a causal relationship between a medicinal product and an adverse event is at least a reasonable possibility, i.e. the relationship cannot be ruled out.

8.1.2 Unexpected Adverse Drug Reaction

An unexpected adverse drug reaction is defined as an adverse reaction, the nature or severity of which is not consistent with the applicable product information.

8.1.3 Assessment of Adverse Events by the Investigator

The Investigator will assess the severity (intensity) of each adverse event as mild, moderate, or severe, and will also categorize each adverse event as to its potential relationship to study drug using the categories of yes or no.

Assessment of Severity:

Mild – An event that is easily tolerated and generally not interfering with normal daily activities.

Moderate – An event that is sufficiently discomforting to interfere with normal daily activities.

Severe – An event that is incapacitating with inability to work or perform normal daily activities.

Causality Assessment:

The relationship of an adverse event to the administration of the study drug is to be assessed according to the following definitions:

No (unrelated, not related, no relation) – The time course between the administration of study drug and the occurrence or worsening of the adverse event rules out a causal relationship and another cause (concomitant drugs, therapies, complications, etc.) is suspected.

Yes (related) – The time course between the administration of study drug and the occurrence or worsening of the adverse event is consistent with a causal relationship and no other cause (concomitant drugs, therapies, complications, etc.) can be identified.

The definition implies a reasonable possibility of a causal relationship between the event and the study drug. This means that there are facts (evidence) or arguments to suggest a causal relationship.

The following factors should also be considered:

- The temporal sequence from study drug administration-
 - The event should occur after the study drug is given. The length of time from study drug exposure to event should be evaluated in the clinical context of the event.
- Underlying, concomitant, intercurrent diseases-
 - Each report should be evaluated in the context of the natural history and course of the disease being treated and any other disease the subject may have.
- Concomitant drug-
 - The other drugs the subject is taking or the treatment the subject receives should be examined to determine whether any of them might be recognized to cause the event in question.
- Known response pattern for this class of study drug-
 - Clinical and/or preclinical data may indicate whether a particular response is likely to be a class effect.

- Exposure to physical and/or mental stresses-
 - The exposure to stress might induce adverse changes in the recipient and provide a logical and better explanation for the event.
- The pharmacology and PK of the study drug-
 - The known pharmacologic properties (absorption, distribution, metabolism, and excretion) of the study drug should be considered.

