8.3 Serious Adverse Event Reporting – Procedures for Investigators

Initial Reports

All SAEs occurring from the time of informed consent until 30 days following the last administration of study drug must be reported within 24 hours of the knowledge of the occurrence (this refers to any adverse event that meets any of the aforementioned serious criteria). All SAEs that the Investigator considers related to study drug occurring after the 30-day Follow-up Period must be reported to the Sponsor.

To report the SAE, complete the appropriate form for the study. It is very important that the form be filled out as completely as possible at the time of the initial report. This includes the Investigator's assessment of causality. Any follow-up information received on SAEs should be forwarded within 1 business day of its receipt. If the follow-up information changes the Investigator's assessment of causality, this should also be noted on the appropriate SAE follow-up form. Preliminary SAE reports should be followed as soon as possible by detailed descriptions including copies of hospital case reports, autopsy reports, and other documents requested by the sponsor. The Investigator must notify his/her Institutional Review Board (IRB) of the occurrence of the SAE, in writing, if required by their institution. A copy of this communication must be forwarded to the Sponsor to be filed in the Sponsor's Trial Master File.

The detailed contact information for reporting of SAEs is provided in the Investigator Study File.

Follow-Up Reports

The Investigator must continue to follow the subject until the SAE has subsided or until the condition becomes chronic in nature, stabilizes (in the case of persistent impairment), or the subject dies.

Within 24 hours of receipt of follow-up information, the Investigator must update the appropriate form for the study and submit any supporting documentation (eg, subject discharge summary or autopsy reports) via fax or e-mail.

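### The Yes and No causality definitions in 8.1.3 leave two kinds of adverse event without a category and conflict with the reaction standard in 8.1.1, so sites can code the same event differently

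*Protocol*

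**What the plan says.** Protocol 8.1.3 gives the investigator two causality categories, Yes and No, and a definition for each.

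- **Yes**: the time course "is consistent with a causal relationship and no other cause (concomitant drugs, therapies, complications, etc.) can be identified".
- **No**: the time course "rules out a causal relationship and another cause (concomitant drugs, therapies, complications, etc.) is suspected".

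Two explanatory sentences follow the Yes definition: "The definition implies a reasonable possibility of a causal relationship between the event and the study drug" and then "This means that there are facts (evidence) or arguments to suggest a causal relationship". After them comes a list of factors to weigh: timing, underlying and intercurrent disease, other drugs, class effects, stress and pharmacology.

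Protocol 8.1.1 sets the standard for an adverse drug reaction. The causal relationship "is at least a reasonable possibility, i.e. the relationship cannot be ruled out". It sets no condition about other causes.

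The call is used in 8.3. The initial SAE form must be as complete as possible: "This includes the Investigator's assessment of causality". For late events, "All SAEs that the Investigator considers related to study drug occurring after the 30-day Follow-up Period must be reported to the Sponsor". Section 8.5 governs expedited reporting of suspected unexpected serious adverse reactions.

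**The concern.** Each definition joins two conditions with *and*, and the two are not complements of each other. Events that meet one condition of each definition have no assigned category, although the investigator must still choose one. The protocol also has two thresholds for the same question: 8.1.1 needs only that the drug cannot be excluded, while the Yes wording in 8.1.3 needs the absence of any other identifiable cause.

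The gap is realistic in this trial. All subjects are due to have an operation on Day 10 (+3 days), subjects with chronic liver disease are enrolled, and 8.1.3 names complications, therapies and concomitant drugs as other causes. A postoperative thrombosis with consistent timing is an example: surgery is an obvious candidate cause, but the drug may not be excluded. Section 1.4.3 reports a portal vein thrombosis judged possibly related in an earlier study. The study has a single arm (5.3), so no control group can show an excess of events if individual attribution is inconsistent.

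**Working it through.** The protocol gives no figure on this point, so the check is logical. The inputs are the two definitions in 8.1.3 and the threshold in 8.1.1. Timing is treated as either excluding the drug or consistent with it. Another cause is treated as present or absent, although the No definition says suspected and the Yes definition says identified.

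| | Time course | Another cause | 8.1.3 as worded | 8.1.1 | Yes strict, otherwise No | No strict, otherwise Yes |
|---|---|---|---|---|---|---|
| A | rules drug out | present | No | not a reaction | No | No |
| B | rules drug out | absent | neither | not a reaction | No | **Yes** |
| C | consistent | present | neither | reaction, if the drug cannot be ruled out | **No** | Yes |
| D | consistent | absent | Yes | reaction | Yes | Yes |

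Bold marks disagreement with 8.1.1.

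1. **Coverage.** Two of four combinations, B and C, have no category.
2. **Yes strict, No as default.** Related = {D}, while 8.1.1 gives {C, D}. The first is a proper subset of the second, so this reading loses related events and cannot add any.
3. **No strict, Yes as default.** Related = {B, C, D}. This agrees with 8.1.1 on C but adds B, an over-count. It also over-counts those events in C where the other cause does exclude the drug, because 8.1.1 would not call them reactions.
4. **Does the rest of 8.1.3 settle B or C?** The first explanatory sentence uses the 8.1.1 threshold and so does not match the Yes wording it follows. The second can be read as asking for positive evidence, which is more than not being able to rule the drug out. The listed factors invite weighing of other causes, but no rule assigns the event to a category.
5. **Size.** Let *s* be the share of 8.1.1 reactions that also have another identifiable cause. The protocol gives no value for *s*. Strict Yes captures 1 − *s* of the 8.1.1 reactions. For assumed values *s* = 0.25, 0.50 and 0.75, this is 75%, 50% and 25%. These show the mechanism and are not estimates.
6. **Where it matters.**
   - Affected: the yes/no code on each adverse event; the causality assessment in each initial SAE report (8.3); SAEs after the 30-day period, which must be reported only if considered related (8.3).
   - Possibly affected: which events are treated as suspected unexpected serious adverse reactions (8.5). Sections 8.1.2 and 8.5 speak of a reaction, the term that 8.1.1 defines, so the looser standard arguably governs there.
   - Not affected: SAE reporting from consent to 30 days after the last dose, which does not depend on causality (8.3); collection of adverse events, which "will be monitored and documented from the time of informed consent until study participation is complete" (8.1); the incidence analysis in 9.2.2; and efficacy.

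**The case against.** The best defence is that 8.1.3 should be read as a whole. The two explanatory sentences can be taken as one gloss that points back to a reasonable possibility. Weighing disease, other drugs and stress would be pointless if any nameable cause automatically barred Yes. Investigators are also briefed on eCRF completion and SAE reporting (11.4), and those materials are not at hand. Section 9.2.2 names no analysis of related events.

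Part of this stands. A sensible investigator may well reach the 8.1.1 answer, which narrows the practical conflict, and nothing planned in 9.2.2 changes. But the protocol says that the relationship is to be assessed according to the two definitions, and the gloss does not remove the condition that no other cause can be identified. Nor can a later analysis plan recover an attribution already made under inconsistent wording.

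A reader might infer that the wording can only under-count related events. The document does not support that. Under-counting follows only if sites apply Yes strictly and default to No; the opposite default is equally open on the text and over-counts. Nor is every event in row C a reaction under 8.1.1, since another cause may rule the drug out.

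**Conclusion.** The point holds as a contradiction in the wording. The categories in 8.1.3 are not exhaustive, and the Yes definition is stricter than the reaction standard in 8.1.1. What follows is inconsistent coding between sites, with a direction that depends on the default each site adopts. This rests on a literal reading of both definitions and on 8.1.1 as the reference; it says nothing about true causality.

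The extent cannot be put in numbers. A reader might take the share of follow-up that falls after the operation as a gauge, but that is a share of time and measures no miscoding; liver disease and concomitant drugs are candidate causes before surgery too. A reader might also infer that the late-SAE route covers at most 3 scheduled days (last dose Day 5 + 30 = Day 35; latest Visit 6 on Day 38; 38 − 35 = 3). That fails for subjects who stop drug early and stay in follow-up under 4.3.1: with the last dose on Day 1 and Visit 6 on Day 38, the gap is 38 − 31 = 7 days, and later events can still reach the investigator.

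The sponsor should correct this because attribution carries weight in a single-arm surgical study. It does not threaten the primary result or the planned incidence tables.

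**What to change.** Put both categories in 8.1.3 on the 8.1.1 standard and make them complementary:

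- **Yes**: a causal relationship is at least a reasonable possibility (it cannot be excluded), even if another cause is also possible.
- **No**: there is no reasonable possibility of a causal relationship, whether or not another cause is suspected.

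Reword the sentence on facts or arguments so that it expresses the same single standard, or delete it. Keep the listed factors as considerations, and align the eCRF guidance.

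The cost is a few sentences in 8.1.3, the eCRF guidance and a second look at events already coded, chiefly those where another cause was noted. The related-event count may look less favourable afterwards. No visit, endpoint, analysis set or sample size changes.

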8.2 Serious Adverse Events

An adverse event or adverse reaction is considered serious if, in the view of either the Investigator or Sponsor, it results in any of the following outcomes:

- Death,
- A life-threatening adverse event,
 - NOTE: An adverse event or adverse reaction is considered “life-threatening” if, in view of either the Investigator or Sponsor, its occurrence places the subject at immediate risk of death. It does not include an event that, had it occurred in a more severe form, might have caused death.
- Requires hospitalization or prolongation of existing hospitalizations,
 - NOTE: Any hospital admission with at least 1 overnight stay will be considered an inpatient hospitalization. An emergency room visit without hospital admission will not be recorded as an SAE under this criterion, nor will hospitalization for a procedure scheduled or planned before signing of informed consent. However, unexpected complications and/or prolongation of hospitalization that occur during elective surgery should be recorded as adverse events and assessed for seriousness. Admission to the hospital for social or situational reasons (ie, no place to stay, live too far away to come for hospital visits) will not be considered inpatient hospitalizations. Hospitalization due to expected recovery time for the planned procedure will not be counted as an SAE.
- A persistent or significant disability/incapacity or substantial disruption of the ability to conduct normal life functions,
- A congenital anomaly/birth defect, or
- An important medical event.
 - NOTE: Important medical events that may not result in death, be life-threatening, or require hospitalization may be considered an SAE when, based upon appropriate medical judgment, they may jeopardize the subject and may require medical or surgical intervention to prevent one of the outcomes listed above. Examples of such medical events include allergic bronchospasm requiring intensive treatment in an emergency room or at home, blood dyscrasias or convulsions that do not result in inpatient hospitalizations, or the development of drug dependency.

8.3 Serious Adverse Event Reporting – Procedures for Investigators

Initial Reports

All SAEs occurring from the time of informed consent until 30 days following the last administration of study drug must be reported within 24 hours of the knowledge of the occurrence (this refers to any adverse event that meets any of the aforementioned serious criteria). All SAEs that the Investigator considers related to study drug occurring after the 30-day Follow-up Period must be reported to the Sponsor.

To report the SAE, complete the appropriate form for the study. It is very important that the form be filled out as completely as possible at the time of the initial report. This includes the Investigator's assessment of causality. Any follow-up information received on SAEs should be forwarded within 1 business day of its receipt. If the follow-up information changes the Investigator's assessment of causality, this should also be noted on the appropriate SAE follow-up form. Preliminary SAE reports should be followed as soon as possible by detailed descriptions including copies of hospital case reports, autopsy reports, and other documents requested by the sponsor. The Investigator must notify his/her Institutional Review Board (IRB) of the occurrence of the SAE, in writing, if required by their institution. A copy of this communication must be forwarded to the Sponsor to be filed in the Sponsor's Trial Master File.

The detailed contact information for reporting of SAEs is provided in the Investigator Study File.

Follow-Up Reports

The Investigator must continue to follow the subject until the SAE has subsided or until the condition becomes chronic in nature, stabilizes (in the case of persistent impairment), or the subject dies.

Within 24 hours of receipt of follow-up information, the Investigator must update the appropriate form for the study and submit any supporting documentation (eg, subject discharge summary or autopsy reports) via fax or e-mail.

8.4 Pregnancy Reporting

If the subject becomes pregnant during the study or within 30 days of discontinuing study drug, the Investigator should report the pregnancy within 24 hours of being notified. Safety will then forward the appropriate form to the Investigator for completion.

A subject becoming pregnant while on study drug will immediately be withdrawn from the study and early termination study procedures will be performed.

The subject should be followed by the Investigator until completion of the pregnancy. If the pregnancy ends for any reason before the anticipated date, the Investigator should notify Safety. At the completion of the pregnancy, the Investigator will document the outcome of the pregnancy. If the outcome of the pregnancy meets the criteria for immediate classification as an SAE (ie, postpartum complication, spontaneous abortion, stillbirth, neonatal death, or congenital anomaly), the Investigator should follow the procedures for reporting an SAE.

8.5 Expedited Reporting

The Sponsor will report all relevant information about suspected unexpected serious adverse reactions that are fatal or life-threatening as soon as possible to the FDA, and in any case no later than 7 days after knowledge by the Sponsor of such a case, and that relevant follow-up information will subsequently be communicated within an additional 8 days.

All other suspected unexpected serious adverse reactions will be reported to the FDA as soon as possible but within a maximum of 15 days of first knowledge by the Sponsor.

The Sponsor will also inform all Investigators as required.

8.6 Clinical Laboratory Evaluations

Clinical safety laboratory assessments will include serum chemistry, hematology, and coagulation and will be obtained as indicated in Appendix A. See Appendix B for a complete list of analytes.

Local laboratories will be used to determine eligibility; however, for study analysis and reporting purposes, only values determined at a central laboratory will be used with the exception of platelet count. Local laboratories may be used if immediate results are clinically needed.

8.7 Vital Signs

Vital sign measurements will include height (at the Baseline Visit only), weight, body temperature, blood pressure, and pulse rate and will be measured after resting for 5 minutes as indicated in Appendix A.

8.8 Physical Examinations

Physical examinations will consist of the following at a minimum: chest, lungs, heart, and abdomen.. Physical examinations will be performed as indicated in Appendix A.

8.9 Demographic and Medical History

Demographic information (date of birth, gender, race, and ethnic group) and relevant medical history will be recorded at the Screening or Baseline Visit.

9 STATISTICS

9.1 Analysis Populations

Full Analysis Set (FAS): The FAS will include all enrolled subjects who receive at least 1 dose of avatrombopag.

Per-Protocol Analysis Set (PPS): The PPS will include the subset of subjects from the FAS who are treated according to the protocol without any major deviations. A full list of major protocol deviations will be finalized prior to database lock.

Safety Analysis Set: The Safety Analysis Set will include all subjects who receive at least 1 dose of avatrombopag.

9.2 Statistical Methods

9.2.1 Analysis of Efficacy

All primary and secondary efficacy endpoints will be analyzed using the FAS. The PPS will be used only for sensitivity analysis of the primary and secondary efficacy endpoints.

